1 INTRODUCTION

1.1 Background

Human Cytomegalovirus (HCMV) infection is widespread and can result in severe sequelae in susceptible populations. HCMV can infect a diverse number of cells resulting in productive viral replication in epithelial, endothelial, fibroblasts, hepatocytes, muscle and neuronal cells. Following primary infection, HCMV finds its way to the hematopoietic progenitor cells in the bone marrow where it enters a life-long latency. Sporadic reactivation from latency is believed to be frequent [[Struble 2021](#)].

Antibody therapy of HCMV provides an alternative to antiviral drugs with an expectation of qualitatively lower toxicity. The leading small molecule antiviral effective against HCMV, ganciclovir (and its oral prodrug formulation valganciclovir), has side effects (including neutropenia, nephrotoxicity, and potential mutagenicity) that make its use problematic for major indications, including congenital transmission or the early post-transplant period for HCT [[Kalil 2009](#)]. Although the recently approved small molecule antiviral letermovir has reduced neutropenic activity and is therefore useful in HCT, it has not eliminated CMV reactivation in adult HCT patients [[Marty 2020](#)].

Antibodies against HCMV gB have long been known to neutralize virus infection in both fibroblasts and epithelial cells [[Meyer 1992](#)]. Antibodies recognizing antigenic determinant (AD)-2 site I on gB mainly mediate this effect [[Baraniak 2018](#)]. Although the AD-2 linear epitope region is highly conserved among clinical isolates of the HCMV, different antibodies against this epitope have different ultra-fine specificity for the epitope [[Lantto 2003](#); [Ohlin 1993](#); [Silvestri 1993](#)]. Of the mAbs cloned by Trellis, TRL345 had the best potency *in vitro*, substantially higher than a well-known human mAb ITC-88 [[McCutcheon 2014](#)]. Antibodies with the specificity of TRL345 are present in CMV-HIG, but only at a level of ~1-2% determined by antigen ELISA.

Vaccines are also in development, but face formidable challenges including adeptness of HCMV in evading the immune system and limited animal models [[Inoue 2018](#)]. A recombinant gB formulated with MF59 adjuvant elicited strong humoral responses and was 50% effective in preventing primary infections in solid organ transplant infants, but with limited durability [[Cui 2019](#)].

1.2 TRL345

TRL345 is a human IgG1kappa (G1m1,17 (z,a); Km3 allotype) monoclonal antibody cloned from human B lymphocytes which targets the highly conserved AD-2, Site I epitope on the gB viral glycoprotein of the Human Cytomegalovirus (HCMV). The short name throughout this document is TRL345. The formal identifying name for TRL345 drug product is TRL345 for intravenous (IV) injection. TRL345 for IV injection is supplied at a nominal concentration of 10 mg/mL in single-

use vials. Each vial contains 10 mL of TRL345 in 20 mM histidine/150 mM sodium chloride/pH 6.0. TRL345 for IV injection is a sterile, clear, colorless, preservative-free liquid concentrate for IV infusion. TRL345 IV will be infused in subjects without further dilution.

The biological activity of TRL345 was characterized by a series of in vitro assays. First, it was found that TRL345 neutralized 15 out of 15 HCMV clinical isolates spanning the viral phylogeny, consistent with the highly conserved nature of the epitope. Second, efficacy against the high pathology clinical isolate VR1814 was established on human foreskin fibroblasts (HFFs), human umbilical vein endothelial cell (HUVEC) and retinal pigmented epithelial cells (ARPE19) with a potency for all cell types of ~0.1 µg/mL. TRL345 activity on a broad range of cell types includes two key specialized placental cell types whose infection in vivo results in deficient growth of the placenta and thus of nutrient deprivation for the developing fetus: placental fibroblasts (maternal origin) and trophoblast progenitor cells (fetal origin). Third, HCMV can also spread by syncytial transfer. TRL345 did not fully prevent syncytial transfer but its efficacy was comparable to CMV-HIG but at ~10-fold lower concentration, and superior to a comprehensive set of other mAbs against various HCMV antigens. Fourth, because there is no adequate animal model for HCMV infection, the efficacy of TRL345 was evaluated using an *ex vivo* model; in this model, cytotrophoblasts grown on soft agar (Matrigel™) emigrate from cell columns to form anchoring villi that mimic the invasion of endometrium in vivo. VR1814 effectively infects these cells causing stunted growth of the invasive villi. To test the efficacy of antibody treatment, explants were infected at 12 hours after plating, treated with either TRL345 or CMV-HIG (human immune globulin) and fixed at 3 days post-infection. Neutralizing activity was measured in infected villous explants by counting the number of VR1814-infected cytotrophoblasts, which were visualized using a fluorescent tagged antibody to the viral immediate early (IE) antigen. TRL345 was ~50-fold more potent than CVM-HIG.

The gB AD-2 site is the most highly conserved region of the entire HCMV genome. The few variants in the TRL345 epitope discovered using next generation sequencing showed nearly all were conservative substitutions. Accordingly, escape from TRL345 is expected to be rare.

1.3 Nonclinical Pharmacology and Toxicology Studies

Summaries of the nonclinical pharmacology, pharmacokinetics, and toxicology studies are provided below. Additional details of the studies can be found in the Investigator's Brochure.

1.3.1 Pharmacology

Human cytomegalovirus (HCMV) is a member of the family Herpesviridae that also includes herpes simplex virus and Epstein-Barr virus. HCMV has co-evolved with humans over an extended timeframe [McGeoch 2000], and although 50-90% of adults are chronically infected with HCMV, it rarely causes harm because it is kept in check by the immune system. However, HCMV can become highly pathogenic in immunocompromised infants and may cause lethal infections,

especially in organ transplant or AIDS infants. Moreover, about 1% of susceptible women acquire a primary infection during pregnancy, with 40% of these women transmitting HCMV to their fetuses, contributing to stillbirth and to neurological defects, most commonly including deafness [Boppana 1995; Duff 2005].

HCMV replicates in vivo and in vitro in many different host cell types including epithelial cells, fibroblasts, connective tissue cells, hepatocytes, various leukocyte populations, and vascular endothelial cells. The broad host cell range makes it unclear if one protein or protein complex in the viral envelope is responsible in mediating entry into the host cell(s). More than 10 glycoproteins have been identified in HCMV particles as playing some role in the virus entry process including the essential glycoproteins gB, gH, gL, gM, and gN. These glycoproteins are being targeted for the development of vaccines or therapeutics (including monoclonal antibodies).

[figure not shown]

Figure 1: HCMV Glycoproteins as Vaccines or Therapeutic Targets

The essential CMV glycoprotein complexes required for cell attachment and entry are depicted. The glycoprotein complex (GC) designations are indicated. The pentameric complex (PC) is illustrated on the right and includes the UL128, UL130, and UL131a proteins. Parallel dashed lines represent disulfide linkages between individual envelope proteins. [Gardner 2016]

HCMV gB is a major envelope glycoprotein of HCMV encoded by the UL55 gene and has been clearly implicated in host cell entry, cell-to-cell virus transmission, and fusion of infected cells. In addition, it is an important target of both humoral and cellular immune responses [Pass 2009; Pöttsch 2011; Pang 2008].

Entry of HCMV into cells requires the conserved glycoprotein B (gB), thought to function as a fusogen and reported to bind signaling receptors. The crystal structure of the HCMV gB ectodomain has been determined to 3.6-Å resolution [Burke 2015]. The structure resembles the post-fusion structures of HSV-1 and EBV homologs. gB has a unique domain arrangement, demonstrating structural plasticity of gB that may accommodate virus-specific functional requirements.

• **Tissue Cross-Reactivity of TRL345 with Human Adult and Neonatal Tissues**

A GLP tissue cross-reactivity study of TRL345 using human adult and neonatal tissues was performed by Charles River Laboratories, (Reno, NV; [Charles River Study # 20082357](#)). The objective of this study was to determine the potential cross-reactivity of TRL345 with cryosections of human adult and neonatal tissues. This work was conducted by Charles River Laboratories under a service agreement with SRI International (Menlo Park, CA). A series of method development experiments was used to elucidate the optimal conditions for binding of TRL345 to control cell line sections. Following completion of the method development, the optimal binding of TRL345 was then applied at concentrations of 5.0 and 50.0 µg/mL. Panel of adult and fetal tissues evaluated are listed in **Table 1**.

Table 1: Panel of Tissues Evaluated for TRL345 Cross-Reactivity

Adult Human Tissues		
Adrenal	Lung	Spinal cord
Blood cells	Lymph node	Spleen
Blood vessels (endothelium)	Ovary	Striated (skeletal) muscle
Bone marrow	Fallopian tube (oviduct)	Testis
Brain, cerebrum (cortex)	Pancreas	Thymus
Brain, cerebellum	Parathyroid	Thyroid
Breast (mammary gland)	Peripheral nerve	Tonsil
Eye	Pituitary	Ureter
Gastrointestinal tract	Placenta	Urinary bladder
Heart	Prostate	Uterus- body (endometrium)
Kidney (glomerulus, tubule)	Salivary gland	Uterus, cervix
Liver	Skin	
Fetal Tissues		
Brain – Cerebral Cortex	Endothelium – Blood Vessels	Kidney
Liver	Lung	Ovary
Pancreas	Spleen	Thymus

Sporadic TRL345 binding was observed on epithelial cells in several adult (colon, skin, small intestine, and pancreas) and fetal (small intestine and pancreas) human tissues.

Consistent TRL345-specific staining (staining of 1 or more samples at 5 and 50 µg/mL) was observed in the cytoplasm, cell membrane and/or nuclei of colonic epithelium (3/3); small intestine epithelium (2/3); intercalated discs of heart myocytes (1/3 at 5 µg/mL; 3/3 at 50 µg/mL); adult liver bile duct epithelium (2/3); adult pancreas duct epithelium (2/3); epidermal keratinocytes, follicular and/or sebaceous gland epithelium, and/or superficial keratin in skin (3/3); cervix epithelium (1/3); bile duct epithelium of neonatal liver (1/3); and in duct epithelium and/or acinar cells of neonatal pancreas (2/2 at 50 µg/mL, 1/2 at 5 µg/mL).

Less consistent staining (1 or more samples at 50 µg/mL only) included cytoplasmic and/or nuclear staining in the granular cell layer of the cerebellum (3/3); corneal epithelium of the eye (2/3); epithelium, smooth muscle and/or fibromuscular cells of the Fallopian tube (3/3); epithelium, particularly gastric pits, smooth muscle cells of the muscularis externa, and submucosal vessels of the stomach (3/3); interstitial spindle cells and tubular epithelium in the kidney (1/3); placental villous mesoderm and endothelium (1/3); and connective tissue stromal cells in the prostate (1/3). Much of this inconsistent staining may be non-specific even though similar staining was not observed in matched negative controls. Staining in tissues with only 1 sample weakly positive at 50 µg/mL only (kidney, placenta, and prostate) is likely to be non-specific and not physiologically relevant.

Non-specific staining in several tissues confused interpretation of possible concurrent specific staining. These tissues included: liver (adult and neonatal), pancreas (adult and neonatal), salivary gland, pituitary, stomach, and skin.

Due to the widespread prevalence of chronic HCMV infection in humans, the observed sporadic binding is presumed to have been due to latent HCMV infections. That is, latent HCMV infection includes slow but persistent replication of the virus [Traylen 2011].

- **Homology of HCMV gB and TRL345 Binding Epitope within Human Proteome**

A BLAST search was performed to determine if any human proteins have significant homology to the HCMV gB protein ([GenBank Protein Accession# CAA35414.1](#)) or to the TRL345 binding epitope (ETIYNTTLKG). The BLAST search using TRL345 binding epitope resulted in over 900 hits. Within the hits, many had the same sequence pattern. All the sequences identified have amino acid substitutions or are missing amino acids that will significantly affect the binding of TRL345. Based on the BLAST search there are no human proteins that contain the TRL345 binding epitope.

To further evaluate potential of cross-reactivity as the source of the sporadic tissue reactivity staining, TRL345 was screened for binding against fixed and permeabilized human HEK293 cells, individually expressing 4417 human proteins comprising a comprehensive catalog of the human cell surface proteome (Retrogenix, Ltd). This screen revealed a set of 8 hits with potential recognition by TRL345, but no such binding could be confirmed. Moreover, the tissue distributions of these proteins did not match the TRL345 staining pattern.

- **Potential Off-Target Protein Binding by TRL345**

To evaluate potential of off-target protein binding as the source of the sporadic human tissue cross-reactivity staining, TRL345 was screened for binding against fixed and permeabilized human HEK293 cells, individually expressing 4417 human proteins comprising a comprehensive catalog of the human cell surface proteome (Retrogenix, Ltd). This screen revealed 8 hits by binding to solubilized cells with potential recognition by TRL345, but no such

binding could be confirmed by flow cytometry on live cells. Moreover, the tissue distributions of these proteins did not match the TRL345 staining pattern.

To further explore the possibility that TRL345 binds human proteins, an immuno-affinity extraction study was conducted. After extracting solubilized human proteins on a sorbent to which TRL345 was conjugated, the eluted proteins were analyzed by mass spectroscopy. Low homology to the TRL345 binding epitope among the eluted proteins was noted in 7 of the 54 unique skeletal muscle proteins (non-staining tissue by immunohistochemistry), 18 of the 197 unique pancreas proteins (positive staining) and 6 of the 414 proteins that were common to both the skeletal muscle and pancreas. The majority of the hit proteins are primarily intracellular. Homology to the TRL345 epitope was minimal for all of these, and none of them matched the tissue distribution of the staining observed in the TCR study.

Moreover, the toxicity study in rats did not reveal any toxicity signals for the gastrointestinal tissues in which binding in the human tissue cross reactivity study was observed. There were no signs of edema, no increase in inflammatory cells, and no abnormalities in clinical and hematology. The sparse binding of TRL345 in the pancreas tissue by immunohistology was only observed with the exocrine tissue (98% of the organ); no binding was observed to beta-cells (insulin producing cells).

The possibility of adverse off-target binding cannot be excluded. The main risk of adverse off-target binding is to the gastrointestinal tissues and pancreas, and includes the possibility of diarrhea, abdominal spasms and discomfort.

1.3.2 *Pharmacokinetics*

TRL345, administered as a single bolus IV injection at 10 mg/mL, was well tolerated in Sprague-Dawley rats. T_{max} occurred 5 minutes after the end of dosing and the C_{max} was 184 $\mu\text{g/mL}$. The elimination curve, accurately described by an open two compartment pharmacokinetic model, showed a short distribution phase with a $t_{1/2\alpha}$ of 3 hours and a longer elimination phase with a $t_{1/2\beta}$ of 46 hours. The volume of distribution (V_d) was approximately equivalent to plasma volume (60 mL/kg); however, the volume of distribution at steady state (V_{ss}), 305 mL/kg, indicated some distribution into the extravascular space. $AUC_{0-\infty}$ was 1,642 $\mu\text{g}\cdot\text{hr/mL}$. These data are consistent with other monoclonal antibodies and do not suggest that TRL345 accumulates in a specific tissue or that there is an “antibody sink.”

1.3.3 *Toxicology*

The expected safety profile of TRL345 reflects three unusual factors. First, TRL345 is an IgG1 antibody that was cloned from human B cells. Comparable antibodies are present in CMV-HIG, which has been extensively tested in clinical trials [[Kagan 2019](#)]. Antibodies with the specificity

of TRL345 are present in CMV-HIG at a level of ~1-2%. In a variety of model systems, TRL345 was more effective than CMV-HIG at 50-fold lower dose.

Second, a human mAb with similar specificity as TRL345, but ~5-fold weaker affinity, successfully completed a Phase 1 clinical trial [TCN-202 from Theraclone, Inc; ClinicalTrials.gov Identifier: [NCT01594437](#)]. TCN-202 given at escalating doses from 1 mg/kg to 50 mg/kg was well tolerated throughout the study, with no dose-limiting toxicities or serious adverse events observed and demonstrated a favorable immunogenicity profile (no anti-TCN-202 antibodies were detected).

Third, antibodies against the same target protein are induced by the gB/MF59 vaccine which was well tolerated in clinical trials [[Griffiths 2011](#)]. In a Phase 2 placebo-controlled trial in solid organ transplant candidates, vaccination with gB plus MF59 adjuvant significantly boosted preexisting antibody levels against antigenic domain AD-2, which was correlated with decreased incidence of viremia [[Baraniak 2018](#)].

The safety of TRL345 was evaluated in a series of non-GLP and GLP in vivo studies. The administration of TRL345, to rats by twice weekly intravenous injection for 8 doses at dose levels of 0, 15, 50 or 150 mg/kg/dose was well-tolerated and did not result in any signs of overt toxicity. Clinical signs suggestive of a hypersensitivity-type reaction were observed after the 8th dose in the 15 and 50 mg/kg/dose animals. These clinical signs were considered secondary to the biological activity of the test item and were consequently not considered to be toxicologically significant. Over the 25-day treatment period, C_{max} , $AUC_{0-tlast}$ and AUC_{INF} values obtained on Day 25 from the Group 2 animals of both sexes were comparable to those obtained on Day 1, suggesting that TRL345 does not accumulate when administered twice weekly over a period of 4 weeks at doses ≤ 15 mg/kg/dose. However, C_{max} , $AUC_{0-tlast}$ and AUC_{INF} obtained on Day 25 from the Group 3 and 4 animals of both sexes were higher than those obtained on Day 1, as evidenced by the $AUC_{0-tlast}$ and AUC_{INF} accumulation ratios (2.1 to 5.9), suggesting that TRL345 has the potential to gradually accumulate when administered twice weekly over a period of 4 weeks at doses ≥ 50 mg/kg/dose.

There were no consistently marked sex-related differences in the measured TK parameters, except for T_{max} which appeared to occur later in males (1 hour post dose) as compared to females (5 minutes post dose). Anti-drug antibodies were detected in 13 out of 42 samples, but the presence of anti-human antibodies in the rat does not appear to have affected the test item's TK profile and is not considered relevant to administration of the human antibody to humans. Overall, there were no TRL345-related, toxicologically significant, effects on any of the other study parameters evaluated. The NOAEL for TRL345 was >150 mg/kg/dose; the safety margin is 15-fold compared to maximum starting human dose (MSHD) of 10 mg/kg and 5-fold compared to the maximum recommended high dose (MRHD) of 30 mg/mL proposed for the Phase 1 study [[Clinical Protocol # TRL345-102](#)].

No genotoxicity studies for TRL345 have been performed. Proteins are not typically considered to possess mutagenic potential based upon the inability to cross intact cell membranes, gain access to cytosolic/nuclear compartments, or integrate with or damage host cell DNA and alter host cell genetic material. Furthermore, there are no impurities contained in the final product formulation at levels high enough to be of mutagenic or carcinogenic concern.

No carcinogenicity studies for TRL345 have been performed. However, there was no evidence of abnormal cell proliferation or immunosuppression in cynomolgus monkeys after dosing with TRL345 IV twice weekly up to 150 mg/kg for 28-Days.

No developmental or reproductive toxicity studies with TRL345 have been performed. However, there was no evidence of macro- or microscopic changes in male or female organs from Sprague-Dawley rats dosed with TRL345 IV twice weekly up to 150 mg/kg for 28 days.

No effects attributable to formulated product were noted in Sprague-Dawley rats dosed with TRL345 IV twice weekly up to 150 mg/kg for 28-Days [ITR Study Report # 72460]. Given the excipients of the formulation buffer (i.e., 20 mM Histidine, 150 mM Sodium chloride, at pH 6.0) TRL345 is not expected to be irritating when administered IV.

1.4 Clinical Trials of Study Drug

No clinical trials of TRL345 have been conducted to date.

2 OBJECTIVES AND ENDPOINTS

2.1 Objectives

2.1.1 *Primary Objective*

- Assess the safety and tolerability of TRL345 when administered intravenously (IV) as a single dose in healthy adult volunteers

2.1.2 *Secondary Objectives*

The secondary objectives are to:

- Characterize the pharmacokinetics (PK) of a single IV infusion of TRL345 overall and by DG
- Assess the immunogenicity of TRL345 as measured by anti-drug antibodies (ADAs)

2.1.3 *Exploratory Objective*

The exploratory objectives are to:

- Explore the pharmacodynamics (PD) of TRL345 in an *ex vivo* study using serum samples to explore the capacity of various concentrations of TRL345 to neutralize HCMV in human serum
- Explore if there are any differences in adverse events, clinical labs, or PK across dose groups to explore if there are any signs of off-target binding of TRL345

2.2 Endpoints

2.2.1 *Safety Endpoints*

- Incidence and severity of abnormal physical exam findings, serum chemistries and hematology, vital signs (temperature, blood pressure, heart rate), adverse events, and incidence of serious adverse events

2.2.2 *Pharmacokinetics*

- C_{max} , C_{min} , CL, Vss, and T1/2 overall and by DG will be determined by ELISA

2.2.3 *Immunogenicity*

- Incidence of baseline and IP-emergent ADA (i.e., anti-TRL345 antibodies) in serum will be determined by ELISA

2.2.4 *Pharmacodynamics*

- The proportion of samples with TRL345 concentrations within prespecified ranges that are associated with neutralization of HCMV in human serum

2.2.5 *Exploration of Possible Off-Target Binding*

- Gastrointestinal and CNS adverse events will be compared across DGs for any qualitative or quantitative differences in such events. LDH, hsCRP, IL-1alpha, estimated AUC, and estimated T1/2 will also be compared across DGs.

3 STUDY DESIGN

3.1 Overall Study Design

This is a Phase 1, first-in-human, double-blind, single ascending dose study to assess the safety, PK, and PD of TRL345 in approximately 16 healthy male and female volunteers. Subjects aged 18-65, inclusive, will be screened.

Subjects will be assigned to a DG and randomized to receive TRL345 or placebo. There will be two dose groups. Each DG will be composed of 8 healthy volunteers; of these 6 will be randomized to receive TRL345 and 2 will be randomized to placebo. Any subject who withdraws before completing the study but after receiving IP may be replaced at the discretion of the Sponsor and in consultation with the Investigator. Any replacement subject will be assigned to receive the same treatment as the subject he or she is replacing.

An established ELISA assay available in commercial laboratories to detect IgG antibodies against CMV will be used to determine serostatus of subjects.

Dosing of the first two subjects (one randomized to TRL345 and one randomized to placebo) in each DG will be done on the same day. Dosing of the other subjects will occur at least 72 hours after the first two subjects have been dosed and following review of the blinded safety data from the first two subjects in the DG by the PI and Sponsor. After all subjects within a DG have completed Day 15, a Safety Monitoring Committee (SMC) will review all available safety data through Day 15 prior to making a recommendation regarding escalation to the next higher DG.

Subjects will be admitted to a Phase 1 research unit prior to the IV administration of a single dose of IP. In order to maintain the blind, subjects will be dosed as follows: DG1 will receive 1 mg/kg of TRL345 or 0.1mL/kg of placebo and DG2 will receive 10 mg/kg of TRL345 or 1mL/kg of placebo. All subjects (randomized to either TRL345 or placebo) will receive IP infused over 60 minutes.

Subjects will be closely monitored for AEs and SAEs, including infusion reactions (IRs), from onset of the infusion through discharge from the Phase 1 research unit. Subjects will be assessed for safety and tolerability, including AEs and SAEs at each follow-up visit after discharge through Day 76. A physical exam, vital signs, and routine clinical lab tests (chemistry and hematology) will be done on Days 1, 2, 3, 8, 15, 29, and 43. An ECG will be done on Days 1 and 8.

Serum for PK will be collected on Days 1 (0, 1, 2, 4, 6, 12 hours after start of infusion), 2 (24 hours after start of infusion) and 3 (48 hours after start of infusion), and on Days 8, 15, 29, 43 and 76. Additionally, serum samples will be taken on Days 1, 8, 29, 43 and 76 for measurement of anti-TRL345 antibody levels. Samples taken on Days 1, 43, and 76 will be analyzed using an electrochemiluminescence assay. Samples collected on Days 8 and 29 will be held for exploratory analysis, if warranted, based on Day 43 and Day 76 ADA analysis results. The proportion of subjects with detectable anti-TRL345 antibody responses prior to dosing and IP-emergent anti-TRL345 antibodies will be reported.

Additional serum samples will be collected on Days 1 (pre-infusion and 1 hour after start of infusion), 15, 29, 43, and 76 for *ex vivo* PD assessments, which will be conducted at [name] lab as defined in a separate protocol, whereby the dosed participants of the study will remain anonymous.

Additional serum samples will also be obtained on Days 1 (pre-infusion), 3, 8, 15, 29, and 43 for possible additional exploratory analyses that may be necessary to further explore any unexpected safety or tolerability observations.

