4. Subjects may not use tobacco or nicotine within 4 hours prior to the ECG. ECG on Day 1 will be performed within 4 hours after completion of the infusion.
5. Serum chemistry at Days 1, 15, and 29 is to include hsCRP and LDH.
6. Subjects must refrain from strenuous exercise within 5 days prior to assessment of creatine kinase
7. An additional 5 mL serum sample will be collected immediately prior to the IP infusion on Day 1 and on Days 3, 8, 15, 29, and 43 and stored for possible exploratory analyses.
8. An established ELISA assay available in commercial laboratories to detect IgG antibodies against CMV will be used to determine serostatus of subjects.
9. Samples for PK will be collected immediately prior to the IP infusion on Day 1 and end of the infusion (60 minutes) \pm 15 minutes, and hours 2 \pm 15 minutes, 4 \pm 15 minutes, 6 \pm 15 minutes, 12 \pm 1 hour, 24 (Day 2) \pm 1 hour, and 48 (Day 3) \pm 1 hour after start of infusion and then on Days 8, 15, 29, 43, and 76.
10. Samples for PD will be collected immediately prior to the IP infusion on Day 1 and end of the infusion (60 minutes) \pm 15 minutes and on Days 15, 29, 43, and 76 for *ex vivo* PD assessments.
11. Samples for ADA will be collected immediately prior to the IP infusion on Day 1 and on Days 8, 29, 43, and 76. ADA samples collected on Days 8 and 29 will be held for exploratory analysis, if warranted.

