6.4.5 Study Day 43 (± 3 days) or Early Termination

The following procedures will be performed:

Targeted physical exam

Vital signs including weight

Laboratory Evaluations:

- Serum chemistry
- Hematology
- Fasting glucose
- Fasting blood insulin level
- NT-proBNP and IL-1 α
- Serum for PK, PD, ADA, and possible exploratory analyses
- Serum pregnancy test in WOCBP

AE assessment

Concomitant medication assessment

Overall status

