Serum samples ADA analysis will be taken on Days 1, 8, 29, 43, and 76 for measurement of anti-TRL345 antibody levels. Samples taken on Days 1, 43, and 76 will be analyzed using an ELISA method. Samples collected on Days 8 and 29 will be held for exploratory analysis, if warranted, based on Day 43 and Day 76 ADA analysis results. The proportion of subjects with detectable anti-TRL345 antibody responses prior to dosing and IP-emergent anti-TRL345 antibodies will be reported.

Serum samples for PD assessment will be collected on Days 1 (pre-infusion and 1 hour after start of infusion), 15, 29, 43, and 76 for ex vivo PD assessments, which will be conducted at [name] lab as defined in a separate protocol, whereby the dosed participants of the study will remain anonymous.

Additional serum samples will also be obtained on Days 1 (pre-infusion), 3, 8, 15, 29, and 43 for possible additional exploratory analyses that may be necessary to further explore any unexpected safety or tolerability observations.

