## **7.2 Immunogenicity Concentrations**

### **Measurements and Collection Schedule**

Blood samples for ADA will be collected and analyzed for all subjects at the following time points:

- Day 1: Baseline
- Days 8 (168 hours post-SOI), 29 (672 hours post-SOI), 43 (1008 hours post-SOI), and 76 (1800 hours post-SOI)

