## **7.3 Data Summarization and Presentation**

The ADA presence will be summarized with frequency counts and percentages for the Immunogenicity Population by treatment (pooled placebo, active treatments, active treatment total) at baseline and each post baseline time point. ADA results will be listed for each subject by time point.

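### The documents disagree on whether Day 8 and Day 29 ADA samples are assayed; under the hold rule, an early leaver with no exit sample is counted as not positive without a post-dose test

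*Protocol*

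**What the plan says.** Two sets of statements concern the same samples.

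**Samples held.** Protocol 3.1 and the synopsis assay Days 1, 43 and 76 by default and keep Days 8 and 29 "held for exploratory analysis, if warranted, based on Day 43 and Day 76 ADA analysis results". SAP 3 repeats the hold and the same default days: "Samples taken on Days 1, 43, and 76 will be analyzed using an ELISA method". (The assay method named there differs from Protocol 3.1; that is a separate matter.) Schedule of Events footnote 11 is looser and does not say which results decide: "ADA samples collected on Days 8 and 29 will be held for exploratory analysis, if warranted". Protocol 6.4.3 and 6.4.4 are equally brief.

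**Samples analysed in everyone.** SAP 7.2 states "Blood samples for ADA will be collected and analyzed for all subjects at the following time points", and the list that follows includes Days 8 and 29. SAP 7.3 summarises ADA presence "at baseline and each post baseline time point". Shells IIST and ADAD both provide for Day 8 and Day 29.

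SAP 9, which records departures from the protocol's planned analysis, does not mention the difference.

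Three further provisions matter:
- The Day 43 visit doubles as the early-termination visit and includes an ADA draw: "Serum for PK, PD, ADA, and possible exploratory analyses" (Protocol 6.4.5).
- The Immunogenicity Population (SAP 4) requires one ADA sample, with no condition that it be post-dose.
- The footnotes to both ADA shells take percentages over all dosed subjects.

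**The concern.** Incidence of IP-emergent ADA is a secondary endpoint (Protocol 2.2.3). Under the hold rule, the decision to test the early samples rests on later results. A subject who is lost before Day 43 and does not attend an exit visit never produces those results. Post-dose serum from that subject may be in storage, yet no provision calls for it to be tested. Loss to follow-up and withdrawal of consent are both foreseen in Protocol 4.3.2.

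The table would not necessarily show the gap. The subject qualifies for the population on the baseline sample and stays in the denominator, so lack of a post-dose test and a negative result have the same effect on the percentage positive. With six active subjects per group, one such subject is a sixth of the evidence.

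The contradiction matters apart from that scenario: the laboratory and the programmer are given different instructions about which samples to test.

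**Working it through.** The plan gives no figure to reproduce: there is no dropout rate, no sample size calculation (Protocol 8.1) and no confidence interval planned for ADA. The check compares the texts, follows one subject through them, and then sizes the effect.

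**1. The texts side by side**

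| Source | Day 8 and Day 29 samples | Condition for testing |
|---|---|---|
| Protocol synopsis, 3.1; SAP 3 | Held | Depends on Day 43 and Day 76 results |
| Protocol Schedule footnote 11, 6.4.3, 6.4.4 | Held | Unspecified need |
| SAP 7.2 | Analysed in all subjects | None |
| SAP 7.3; shells IIST, ADAD | Reported at each time point | None |
| SAP 9 | Not listed as a change | – |

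The first and third rows cannot both be followed.

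**2. One subject under each reading**

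Take a dosed subject who gives Day 1 and Day 8 samples, perhaps Day 29, and is then lost before Day 43 with no exit visit.
- If SAP 7.2 governs, the stored samples are assayed and there is no gap.
- If the hold rule governs per subject, there is no Day 43 or Day 76 result to act on, so nothing calls for testing.
- If the hold rule governs study-wide, other subjects' results could release the samples. If all completers are negative, nothing does.

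The documents do not say whether the trigger is per subject or study-wide. They also do not say whether an early-termination sample is assayed: the default list names only Days 1, 43 and 76, and the shells have no early-termination row.

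**3. Effect on the reported percentage**

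Inputs: 6 active subjects per group and 2 groups (Protocol 3.1), so 2 × 6 = 12 active in all; denominator = subjects dosed (shell footnotes). Let n be the number dosed and x the positives observed. The table reports x/n. If one leaver without a post-dose test was in fact positive, the truth is (x + 1)/n, a difference of 1/n.

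| n | x | Reported, x/n | If the leaver was positive, (x + 1)/n | Over subjects with a post-dose result, x/(n − 1) |
|---|---|---|---|---|
| 6 | 0 | 0/6 = 0% | 1/6 = 16.7% | 0/5 = 0% |
| 6 | 1 | 1/6 = 16.7% | 2/6 = 33.3% | 1/5 = 20.0% |
| 12 | 1 | 1/12 = 8.3% | 2/12 = 16.7% | 1/11 = 9.1% |

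**4. How often it could arise**

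Assume each active subject independently has probability d of loss before Day 43. The chance of at least one loss among 12 is 1 − (1 − d)^12:
- d = 5%: 1 − 0.95^12 = 46%
- d = 10%: 1 − 0.90^12 = 72%
- d = 15%: 1 − 0.85^12 = 86%

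These rates are assumptions. For each, the result is an upper bound on the chance of the problem, because only losses with a stored Day 8 or Day 29 sample and no exit sample count.

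**The case against.** The strongest reply is that a reader might infer from the hold rule that these samples can never be tested, and the documents do not say that. SAP 7.2, SAP 7.3 and the shells have them analysed for everyone; the trigger may be study-wide; and nothing forbids testing a lost subject's samples, which are held rather than destroyed. This stands. What can be said is narrower: the texts conflict, and under one side of the conflict no rule requires the test.

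The affected subject is also uncommon. A leaver who attends the exit visit gives an ADA sample. The protocol allows a withdrawn subject to be replaced (4.3.3). The first point stands, subject to the open question of whether that sample is assayed. Replacement is optional and does not recover the leaver's own result.

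Shell ADAD has a row for unevaluable results, which might expose the subject. However, its footnotes do not say whether a sample never drawn or never assayed belongs there, and the in-text shell IIST has no such row. The reduced-denominator rule for missing data sits in SAP 8 on safety, while the ADA shells specify dosed subjects.

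A reader might also infer that leavers are likelier to be ADA-positive, for example because they left after a hypersensitivity reaction. The documents do not show this. Dosing is single, so leaving avoids no further dose; adverse events are followed to resolution, stabilisation or an agreed time (Protocol 7.1, 7.7); and the consent-withdrawal reason in Protocol 4.3.2 excludes adverse events.

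**Conclusion.** The contradiction between Protocol 3.1 with SAP 3 and SAP 7.2 with 7.3 and the shells is certain. The gap for early leavers is conditional: it exists if the hold rule governs, and only for a dosed subject with a stored post-dose sample and no Day 43, Day 76 or early-termination result. For one such subject who was truly positive, the group percentage is understated by one sixth (16.7 percentage points), or one twelfth (8.3 points) across all active subjects. This assumes that the shell footnotes are applied as written.

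A reader might instead express the loss as wider uncertainty, comparing exact 95% upper limits for 0/5 and 0/6: 1 − 0.025^(1/5) = 52% against 1 − 0.025^(1/6) = 46%. That is not what this plan would report. Its denominator is subjects dosed, so the table would show 0/6, and no interval is planned. The reportable effect is an unmarked non-positive, not a wider limit.

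Severity is minor. The study is small and descriptive, the frequency is unknown, and no link between leaving and ADA status is shown. It is still worth changing, because data already in storage would replace an assumption.

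**What to change.** 1. Decide which rule governs, and align the synopsis, Protocol 3.1, Schedule footnote 11, Protocol 6.4.3 and 6.4.4, SAP 3, 7.2 and 7.3, and the Day 8 and Day 29 rows of shells IIST and ADAD. If testing everyone at all time points is intended, amend the protocol or record the departure in SAP 9.
2. If the hold rule is kept, say whether its trigger is per subject or study-wide, make the Day 8 and Day 29 table rows conditional on testing, and add wording such as: *Early-termination ADA samples will be assayed. For any dosed subject without an evaluable ADA result from Day 43 or later, or from early termination, the stored Day 8 and Day 29 samples will be assayed where consent permits, and the day of the last assayed sample will be shown.*
3. Report IP-emergent ADA incidence over subjects with at least one post-dose ADA result, and state how many dosed subjects have none.

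The cost is wording in both documents and at most two extra assays per such leaver, on samples already collected. An early negative is weaker evidence than one at Day 43 or Day 76, which is why the day of the last sample should appear. The hold rule would remain unchanged for all other subjects.
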